6.7. Efficacy Analyses

A descriptive summary will be performed for efficacy endpoint.

- 1) On-demand treatment (surgery)
 - ① The best responses to all the injection of the Xyntha Solofuse prefilled syringe used to treat bleeding (4 point scale: excellent, good, moderate, and no response) will be presented in frequency and percentage.
 - ② Number of observations of less than expected therapeutic effect (LETE) will be presented by n, mean, SD, median, minimum and maximum or frequency and percentage.
 - ③ Mean infusion dosage will be presented by n, mean, SD, median, minimum and maximum.
- 2) On-demand treatment (bleeding)
 - ① The best responses to all the injection of the Xyntha Solofuse prefilled syringe used to treat bleeding (4 point scale: excellent, good, moderate, and no response) will be presented in frequency and percentage.
 - ② Number of observations of less than expected therapeutic effect (LETE) will be presented by n, mean, SD, median, minimum and maximum or frequency and percentage.
 - ③ The number of infusions of Xyntha Solofuse prefilled syringes used to treat each new bleeding episode is descriptive statistics of medication treatment duration will be presented in n, mean, SD, median, minimum and maximum or frequency and

Statistical Analysis Plan for rPMS

percentage.

- ④ Mean infusion dosage will be presented by n, mean, SD, median, minimum and maximum.

3) Prophylactic Therapy

- ① Subjects who have experienced bleeding (overall, spontaneous) will be presented in frequency and percentage.

- ② Annualized Bleeding Rates (ABRs)

The annualized bleeding rate is the incidence rate of bleeding per year. Since the follow up period for each patient is 6 months (= 0.5 year), the ABR is calculated as follows.

N=Number of patients who received prophylactic treatment.

X=Number of patients who have bleeding among the patients included in the patients who received prophylactic treatment

$$ABRs = \frac{X}{N \times 0.5}$$

- ③ Number of observations of less than expected therapeutic effect (LETE) will be presented by n, mean, SD, median, minimum and maximum or frequency and percent.
- ④ Mean infusion dosage will be presented by descriptive statistics as n, mean, SD, median, minimum and maximum.
- ⑤ Total factor consumption (total infusion dosage) will be presented by descriptive statistics as n, mean, SD, median, minimum and maximum.

4) Overall efficacy assessment will be classified as effective/not-effective as follows, presented in frequency and percentage of it.

- ① On-demand treatment

- [Effective]: Subjects with whom the best responses 'Excellent' or 'Good' or 'Moderate'.
- [Not-effective]: Subjects with whom the best responses 'No response'.

- ② Prophylactic Therapy

- [Effective]: Subjects who haven't experienced any atypical bleeding within 48 hours after administration of the Xyntha Solofuse Prefilled Syringe.
- [Not-effective]: Subjects who have experienced at least once atypical bleeding within 48 hours after administration of the Xyntha Solofuse Prefilled Syringe.

5) Efficacy assessment by demographics and baseline characteristics

Classified overall assessment (effective/not-effective) will be presented in frequency and percentage based on categorical variables of demography and baseline characteristics (sex, age group, past/present disease status, renal/hepatic disorder status). To identify statistically significant difference of frequency distribution of classified overall assessment (effective/not-effective) among demography and baseline characteristics, Chi-square test or Fisher's exact

Statistical Analysis Plan for rPMS

test will be performed.

- 6) Efficacy assessment by concomitant treatment (Concomitant Treatments/Therapy status)
Classified overall assessment (effective/not-effective) will be presented in frequency and percentage for concomitant treatment status (Concomitant Treatments/Therapy status). To identify statistically significant difference of frequency distribution of classified overall assessment (effective/not-effective) among concomitant treatment status, concomitant therapy status, Chi-square test or Fisher's exact test will be performed.
- 7) Analysis of factors that affect efficacy
Logistic regression analysis of multivariate analysis will be performed and presented an odds ratio with 95% confidence interval to identify the factors that affect classified overall assessment (effective/not-effective) in demography and baseline characteristics of the patients (sex, age group, past/present disease status, renal/hepatic disorder status), or concomitant treatment status, concomitant therapy status, etc.

7. Reporting Principles

All results of analysis will be reported table and graph to assist the understanding for the study results. Continuous variables will be summarized by descriptive statistics (n, mean, SD, median, minimum and maximum) and categorical variables will be presented in frequency and percentage (n, %). Summary statistics including n, mean, SD, median, minimum and maximum, frequency, etc will be reported to two decimal places using rounding off.

The p-values through the statistical test will be reported to four decimal place and if p-values smaller than 0.0001 will be written as '<0.0001'.

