7.2.4. Administration and Dosage

This drug should be initiated under the supervision of a physician experienced in the treatment of hemophilia A.

This drug is appropriate for use in adults and children of all ages, including newborns.

Formula

$$\begin{array}{rclclclcl} \text{Required} & = & \text{body} & \times & \text{desired factor VIII rise} & \times & 0.5 \\ \text{units} & & \text{weight} & & \text{(IU/dL or normal \%)} & & \text{(IU/kg per IU/dL)} \\ & & \text{(kg)} & & & & \end{array}$$

Precise monitoring of the replacement therapy by means of plasma factor VIII activity assay should be considered, particularly for surgical intervention.

Dosing for Bleeding and Surgery

In the cases of the following hemorrhagic events, consideration should be given to maintaining the factor VIII activity at or above the plasma levels (in % of normal or in IU/dL) for the indicated period, as outline in the following table.

<Maintenance of Factor VIII Activity for Various Hemorrhagic Events>

Degree of Hemorrhage/ Type of surgical procedure	Factor VIII Level Required (% or IU/dl)	Frequency of Doses (hours) /Duration of Therapy (days)
Bleeding Early hemathrosis, minor muscle or oral bleeds	20-40	Repeat every 12 to 24 hours as necessary until resolved. At least 1 day, depending upon the severity of the bleeding episode.
Bleeding into muscles. Bleeding into the oral cavity. Mild head trauma.	30-60	Repeat infusion every 12 to 24 hours for 3-4 days or until adequate local hemostasis is achieved.
Gastrointestinal bleeding. Intracranial, intra-abdominal or intrathoracic bleeding. Fractures.	60-100	Repeat infusion every 8 to 24 hours until bleeding is resolved.
Surgery Minor operation (including tooth extraction)	30-60	Repeat infusion every 12 to 24 hours for 3-4 days or until adequate local hemostasis is achieved. For tooth extraction, a single infusion plus oral antifibrionlytic therapy within 1 hour may be sufficient.
Major operation	60-100	Repeat infusion every 8 to 24 hours until threat is resolved, or in the case of surgery, until adequate local hemostasis and wound healing are achieved. Then continue therapy for at least another 7 days to maintain the factor VIII activity at 30 to 60% (IU/dl)

Dosage for Prophylaxis

This drug has been administrated prophylactically in a pivotal clinical trial in adolescent and adult previously treated patients at a dose of 30 ± 5 IU/kg given 3 times weekly.

Administration

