7.2.5. Study Procedures

The investigator collects data on the Xyntha Solofuse prefilled syringe retrospectively by recording the data in the case report form from the initial administration day up to 6 months from patients who have been administered the Xyntha Solofuse prefilled syringe at least once or are scheduled to be administered the Xyntha Solofuse prefilled syringe.

This study does not have scheduled visit dates because it is not an interventional study. Safety data will be collected at each visit. If a study subject experiences bleeding episodes during the up to 6-month observation period, the clinical response to the treatment required for each bleeding episode will be evaluated.

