7.3.4. Efficacy Evaluation

On-demand treatment (surgery and bleeding)

The study subjects (or caregivers) will be given a general explanation on keeping a diary during the routine treatment situation for the purpose of clinical use. The investigator prepares medical data based on the diary written by the patient. The case report form will

be prepared based on these. For efficacy, data rated on a 4-point rating scale of “excellent”, “good”, “moderate” or “no response” will be collected retrospectively based on the criteria below:

- *Excellent*: Definite pain relief and/or improvement in signs of bleeding starting within 8 hours after an infusion, with no additional infusion administered. Point = 1.
- *Good*: Definite pain relief and/or improvement in signs of bleeding starting within 8 hours after an infusion, with at least one additional infusion administered for complete resolution of the bleeding episode.

Or,

Definite pain relief and/or improvement in signs of bleeding starting after 8 hours after an infusion, with no additional infusion administered. Point = 2.

- *Moderate*: Probable or slight improvement starting after 8 hours following the infusion, with at least one additional infusion administered for complete resolution of the bleeding episode. Point = 3.
- *No Response*: No improvement at all between infusions or during the 24 hour interval following an infusion, or condition worsens. Point = 4.

For efficacy of each infusion of the Xyntha Solofuse prefilled syringe in on-demand treatment, data rated 24 hours after the infusion or immediately before the next infusion are collected retrospectively.

Prophylactic Therapy

The study subjects (or caregivers) will be given a general explanation on keeping a diary during the routine treatment situation for the purpose of clinical use. The investigator prepares medical data based on the diary written by the patient. The case report form will be prepared based on these. Rating data of details on atypical bleeding occurring within 48 hours from administration of the Xyntha Solofuse prefilled syringe by dosage for the prevention of bleeding (spontaneous/at traumatic) are rated and collected retrospectively. (Namely, “occurred” or “not occurred” and the number of bleeding episodes if “occurred”).

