4.7. Efficacy Endpoints

1) On-demand treatment

- ① Responses to all the injection of the Xyntha Solofuse prefilled syringe used to treat bleeding (4 point scale: excellent, good, moderate, and no response)
 - Excellent: Definite pain relief and/or improvement in signs of bleeding starting within 8 hours after an infusion, with no additional infusion administered. Point = 1.
 - Good: Definite pain relief and/or improvement in signs of bleeding starting within 8 hours after an infusion, with at least one additional infusion administered for complete resolution of the bleeding episode. Or, definite pain relief and/or improvement in signs of bleeding starting after 8 hours after an infusion, with no additional infusion administered. Point = 2.
 - Moderate: Probable or slight improvement starting after 8 hours following the infusion, with at least one additional infusion administered for complete resolution of the bleeding episode. Point = 3.
 - No Response: No improvement at all between infusions or during the 24 hour interval following an infusion, or condition worsens. Point = 4.
- ② Number of observations of less than expected therapeutic effect (LETE)
 - If the response to treatment of Xyntha solofuse prefilled syringe assess "no

Statistical Analysis Plan for rPMS

response" after each infusion of 2 consecutive infusions within 24 hours after on-demand treatment, LETE will be calculated once, if it assess "no response" after each infusion of 3 consecutive infusion within 24 hour, LETE will be calculated twice

- ③ In case of bleeding: The number of infusions of Xyntha Solofuse prefilled syringes used to treat each new bleeding episode will be rated.
 - ④ Mean infusion dosage
- 2) Prophylactic Therapy
- ① Percentage of the study subjects who have experienced bleeding (overall, spontaneous)
 - ② Annualized Bleeding Rates (ABRs)
 - ③ Number of observations of less than expected therapeutic effect (LETE)
 - If atypical bleeding occur within 48 hours after administration of the Xyntha Solofuse Prefilled Syringe by dosage for the prevention of bleeding (spontaneous/at traumatic), LETE will be calculated once.
 - ④ Mean infusion dosage
 - ⑤ Total factor consumption (Total infusion dosage)

5. General Consideration

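### SAP 6.7 tabulates only the best on-demand response, not the all-injection ratings defined in the protocol and SAP 4.7, and then classes subjects by that best response

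*SAP*

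**What the plan says.** SAP 4.7 lists the on-demand endpoint as "Responses to all the injection of the Xyntha Solofuse prefilled syringe used to treat bleeding", on a scale from 'Excellent' (1 point) to 'No response' (4 points). Protocol 7.3.3 and 7.7.1 give the same definition. Protocol 7.3.4 sets the rating unit: "For efficacy of each infusion of the Xyntha Solofuse prefilled syringe in on-demand treatment, data rated 24 hours after the infusion", or else just before the next infusion. Protocol 7.2.5 adds another level: if a subject bleeds, "the clinical response to the treatment required for each bleeding episode will be evaluated".

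The analysis section differs. For surgery and for bleeding alike, SAP 6.7(1) and (2) present "The best responses to all the injection of the Xyntha Solofuse prefilled syringe used to treat bleeding" by frequency and percentage. Neither item says whether 'best' is taken per subject, per episode or per operation, or what the percentage is a percentage of.

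SAP 6.7(4) does name the subject as its unit. On-demand 'Effective' means a best response of 'Excellent', 'Good' or 'Moderate'. 'Not-effective' is "Subjects with whom the best responses 'No response". This two-way class is the outcome for the tests in 6.7(5) and (6) and the logistic regression in 6.7(7).

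**The concern.** If SAP 6.7 is programmed as written, the endpoint that SAP 4.7 defines is never reported. The ratings are collected for every infusion, but only the most favourable one in each unreported unit reaches a table. Isolated failures disappear, and so does the split between 'Excellent', 'Good' and 'Moderate' among the other infusions. Two programmers could also choose different units and produce different tables.

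The subject-level class has a second problem. Because 'No response' is the worst category, a best response of 'No response' leaves no room for any other rating. The class therefore answers whether the subject responded at least once, while its label suggests that treatment worked overall. It also depends on how many infusions a subject had, and it may leave few 'Not-effective' subjects for the factor analyses that use it as their outcome.

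**Working it through.** The documents state no response rate, number of infusions per subject or within-subject correlation, so there is no planned figure to reproduce. The check has a logical part and an illustrative part.

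**Logic.** Let a subject have m rated infusions, of which s are not 'No response'.

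- Best response is the lowest score. It equals 4 only if all m scores are 4, that is, s = 0.
- The 6.7(4) class, read per subject, is therefore 1 ('Effective') if s ≥ 1 and 0 if s = 0.
- The subject's own success proportion is s/m. Since s/m ≤ 1, and both are 0 when s = 0, the class is never below s/m. It is above s/m whenever 0 < s < m.
- With m = 1 the two are identical.

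**Example from the documents' own rules.** Suppose three successive infusions within 24 hours are each rated 'No response'. SAP 4.7 provides for this case: "after each infusion of 3 consecutive infusion within 24 hour, LETE will be calculated twice". A fourth infusion is then rated 'Good' under the second limb of that category: "Definite pain relief and/or improvement in signs of bleeding starting after 8 hours after an infusion, with no additional infusion administered". The subject is 'Effective' with s/m = 1/4 = 25%. Similarly, nine 'No response' ratings and one 'Moderate' give a best score of 3, so 'Effective', although 9/10 = 90% of ratings were failures.

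**Illustration (all inputs assumed).** Let q be the probability of 'No response' per infusion, m the number of rated infusions for every subject, and ρ the within-subject correlation.

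- Independent ratings: P(Not-effective) = q^m.
- Correlated ratings (beta-binomial): P(Not-effective) = product over i = 0 to m−1 of (a+i)/(a+b+i), with a = q(1−ρ)/ρ and b = (1−q)(1−ρ)/ρ.

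For q = 0.20 and ρ = 0.75, a = 0.0667 and b = 0.2667.

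- m = 2: 0.2 × (1.0667/1.3333) = 0.160
- m = 5: 0.160 × (2.0667/2.3333) × (3.0667/3.3333) × (4.0667/4.3333) = 0.1224

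For q = 0.20 and ρ = 0, the values are 0.2² = 0.040 and 0.2⁵ = 0.00032.

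| q | m | Infusions not 'No response' | 'Effective', ρ = 0.75 | 'Effective', ρ = 0 |
|---|---|---|---|---|
| 20% | 1 | 80% | 80% | 80% |
| 20% | 2 | 80% | 84.0% | 96.0% |
| 20% | 5 | 80% | 87.8% | 99.97% |
| 10% | 5 | 90% | 94.3% | 99.999% |
| 30% | 5 | 70% | 80.4% | 99.8% |

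**Direction against a pooled rate.** Infusion counts will vary in practice, and the ordering can then reverse. Take one subject with a single 'No response' and another with ten 'Good' ratings. 'Effective' is 1/2 = 50%, while 10/11 = 90.9% of infusions succeeded.

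**The case against.** Several points on the other side are fair.

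- **The unit can be inferred.** SAP 6.7(4) speaks of subjects, and the analysis sets are made up of subjects, so per subject is the natural reading of 6.7(1) and (2). This stands in part: the gap is confined to those two items. They still give no denominator. If 'best' were instead taken per episode, 6.7(4) has no rule for combining episodes. That every infusion must fail follows from the per-subject reading; the SAP does not say it in words.
- **The SAP may amend the plan.** Protocol 7.7.2.2 allows this, and a best response can be seen as one summary over all injections. But SAP 4.7 keeps the all-injection definition without that qualifier, and no reason for the narrower summary is given.
- **Failures remain visible elsewhere.** LETE counts and infusions per bleed are reported in 6.7. On-demand LETE, however, needs consecutive failures within 24 hours, so it misses isolated ones and says nothing about the other three categories.
- **The consequence is limited.** Efficacy is a secondary, descriptive aim in a non-comparative study with no sample-size calculation. This stands.

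Two stronger readings are tempting. One is that the best-response percentage must exceed the infusion success rate. It cannot fall below each subject's own proportion, but the documents do not define that proportion as the endpoint, and the pooled comparison above can go the other way. The other starts from the dosing table, which for serious bleeds says "Repeat infusion every 8 to 24 hours until bleeding is resolved", and concludes that almost every subject will be 'Effective' whatever the failure rate. The documents do not support a model in which infusions stop at the first response: the first limb of 'Good' and the whole of 'Moderate' involve at least one further infusion. They also give no data on how a series ends.

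**Conclusion.** The point holds and should be corrected. SAP 6.7 does not report the on-demand endpoint that the protocol and SAP 4.7 define, and its subject-level class counts a single response among any number of failures as success. That class also carries the on-demand factor analyses in 6.7(5) to (7).

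The size cannot be derived from the documents. Under the assumed 20% failure per infusion and equal infusion counts, the class overstates the 80% infusion figure by 4.0 to 16.0 percentage points at 2 infusions and by 7.8 to about 20 points at 5. The difference is nil at one infusion per subject. These figures rest on the assumed failure rate, infusion count and correlation, and on the per-subject reading of 'best'. The mismatch between 4.7 and 6.7 and the missing denominator depend on none of these assumptions.

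**What to change.** - **SAP 6.7(1) and (2):** tabulate the 4-point rating for all infusions, with the number of infusions as denominator, separately for surgery and bleeding. Add a summary per bleeding episode, as protocol 7.2.5 calls for, and write down how the ratings within one episode are combined.
- **Best response:** state its unit and denominator, and keep it as a supplementary table.
- **SAP 6.7(4), on-demand:** report a result based on all ratings, for example the per-subject proportion of infusions not rated 'No response', beside the best-response class. Label that class 'at least one response'.
- **SAP 6.7(5) to (7):** for on-demand treatment, do not rest the factor analyses on the best-response class alone.

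The cost is SAP wording and modest programming, since the protocol already has each infusion rated and collected. The downside is some added output, chiefly one more table, and an on-demand figure that will probably, though not certainly, look less favourable.

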2.2. Study Design

In this open-label, non-comparative, observational, non-interventional, retrospective and multi-center study, post-marketing surveillance data will be collected retrospectively for up to 6 months from the initial administration day of the Xyntha Solofuse prefilled syringe injected into patients who have been administered the Xyntha Solofuse prefilled syringe (as part of routine treatment at the Korean health care center which has certified investigators). If the study subject has not completed the 6-month treatment, relevant data should be collected based on the medical records within the 30 days after the last administration of the drug.

Statistical Analysis Plan for rPMS

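### The SAP's annualized bleeding rate counts patients who bled, not bleeds, and gives everyone half a year, so it cannot exceed 2.0 and is biased low

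*SAP*

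**What the plan says.** SAP section 6.7, part 3 (prophylactic therapy), item 2 states the intended quantity: "The annualized bleeding rate is the incidence rate of bleeding per year". It then gives the ingredients: "N=Number of patients who received prophylactic treatment" and "X=Number of patients who have bleeding among the patients included in the patients who received prophylactic treatment". The time element is justified by the statement "Since the follow up period for each patient is 6 months (= 0.5 year), the ABR is calculated as follows", and the ABR is set to X/(N × 0.5).

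The design section of the same document (SAP 2.2, matching Protocol 7.1) describes follow-up differently: "data will be collected retrospectively for up to 6 months from the initial administration day". For those who stop early it adds "If the study subject has not completed the 6-month treatment, relevant data should be collected based on the medical records within the 30 days" following the last dose. SAP 2.3.1 admits patients after a single administration.

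Item 1 of the same list in SAP 6.7 already reports the number and percentage of prophylaxis patients with any bleed. The protocol (7.3.3 and 7.7.1) lists ABRs without a formula, so the SAP formula is the only definition. On episode counts under prophylaxis, Protocol 7.3.4 asks whether bleeding occurred "and the number of bleeding episodes if" it did, but that sentence concerns atypical bleeding within 48 hours of a dose.

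**The concern.** The formula does not compute what the line above it defines. An incidence rate of bleeding needs events over time at risk. This formula has patients with at least one event over a nominal time.

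The ABR is the only rate endpoint for prophylaxis. It would go to the regulator under a label that readers take to mean bleeds per patient per year. As written, a product that controlled bleeding poorly could not show a value above 2. The shortfall also grows as the true bleeding rate rises and as more patients stop early, so the figure is least reliable where it matters most.

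**Working it through.** The SAP states no numerical ABR, so there is no figure to reproduce. The check evaluates its formula and compares it with episodes divided by person-years.

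**Ceiling (no assumptions).** X counts patients, so 0 ≤ X ≤ N. At X = N the formula gives N/(0.5N) = 2.0 for any N. In general X/(0.5N) = 2 × (X/N), which is exactly twice the proportion who bled on the same denominator.

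**Direction.** X is never larger than the number of episodes. N × 0.5 is never smaller than the true person-time when nobody is followed beyond six months. Both errors therefore act downward. They vanish only if no patient bleeds twice and everyone has the full six months.

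**Numerator error (assumed true rate L per year, full 0.5 year for all).** With Poisson bleeds, P(any bleed) = 1 − exp(−0.5L), so the expected SAP value is 2(1 − exp(−0.5L)). With negative binomial bleeds and dispersion 1 it is 2(1 − 1/(1 + 0.5L)).

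| True ABR | SAP value, Poisson | Share of true rate (Poisson) | SAP value, negative binomial |
|---|---|---|---|
| 1 | 0.79 | 79% | 0.67 |
| 2 | 1.26 | 63% | 1.00 |
| 4 | 1.73 | 43% | 1.33 |
| 6 | 1.90 | 32% | 1.50 |
| 10 | 1.99 | 20% | 1.67 |

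**Denominator error (assumed follow-up).** A patient observed for 2 months is credited with 0.5/(2/12) = 3 times the actual time. If 30% were observed for 2 months and 70% for 6 months, mean time is 0.3 × 2/12 + 0.7 × 0.5 = 0.40 year, and 0.5/0.40 = 1.25, so person-time is overstated by 25%. With episodes counted correctly but 0.5 year kept, the result is 95% to 75% of the true rate if 10% to 50% of patients have only 3 months, and 92% to 58% if they have only 1 month.

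**Both together.** At a true rate of 4 with 20% of patients followed for 3 months: [0.8 × (1 − exp(−2)) + 0.2 × (1 − exp(−1))]/0.5 = 1.64.

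**Worked example (invented data).** Ten patients have 0, 0, 0, 0, 1, 1, 2, 3, 4 and 5 episodes. The first eight are followed for 0.5 year and the last two for 0.25 year.

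- SAP formula: 6/(10 × 0.5) = 1.20 per year.
- Episodes over the fixed half-year: 16/5 = 3.20.
- Episodes over actual person-years: 16/4.5 = 3.56.

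**The case against.** The core cannot be rebutted, because nothing elsewhere in either document replaces X or the 0.5. Several points around it deserve weight.

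- **Importance.** The ABR is one of five descriptive prophylaxis items under a secondary objective; the primary objective is detection of factor VIII inhibitors. It is not tested and does not feed the effective/not-effective classification or the logistic model. Poor control is not wholly hidden, since the percentage who bled and the counts of less-than-expected therapeutic effect are also reported. This stands, but those counts cover only atypical bleeds within 48 hours of a dose, and no other planned output shows how often prophylaxis patients bled overall.
- **Size.** The documents give no expected bleeding rate, dispersion or follow-up distribution. This stands: only the ceiling and the direction follow from the text.
- **Data availability.** The episode count named in Protocol 7.3.4 is limited to the 48-hour window. This stands as a condition on the fix. Protocol 7.2.5 does have the response to treatment evaluated for each bleeding episode, so counting episodes looks feasible.
- **Data cut-off.** Protocol section 4 ends data collection on 30 September 2017, which would leave anyone first dosed after about 30 March 2017 short of six months. Protocol 7.2.3 runs the study to 30 March 2018, so this is only supporting evidence. The conclusion does not need it.
- **Overrun.** If the 30-day window carried a late stopper slightly past six months, the time error for that patient would reverse. This is minor and leaves the ceiling untouched.

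**Conclusion.** The concern holds, and the formula must be corrected before any ABR is reported. It contradicts the SAP's own definition, duplicates the percentage who bled, and is capped at 2.0 whatever the data. The fixed half-year contradicts the design section. The value is biased low whenever any patient bleeds more than once or is observed for less than six months, subject to the minor overrun exception.

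The magnitude is illustrative. Under Poisson bleeding with full follow-up, a true ABR of 4 would be reported at 43% of its value and a true ABR of 10 at 20%. Overdispersion or early stopping would lower the figures further. The case for correction is that a named endpoint would be mislabelled; the study's primary conclusion does not depend on it.

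**What to change.** In SAP 6.7, part 3, item 2:

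1. Delete the sentence giving every patient six months of follow-up, and the X/(N × 0.5) formula.
2. Define each subject's ABR as the number of bleeding episodes on prophylaxis divided by (days observed on prophylaxis/365.25). Report n, mean, SD, median, minimum and maximum.
3. Report the pooled rate, total episodes divided by total patient-years on prophylaxis, showing both totals. A 95% CI that allows for overdispersion (negative binomial with a log person-time offset) is a useful addition. It goes beyond the descriptive summary now planned, and the correction does not depend on it.
4. Do this for overall and for spontaneous bleeds. Keep X/N only as the percentage who bled.
5. Confirm that the CRF or charts hold counts of all bleeds on prophylaxis, with the spontaneous/traumatic distinction, and not only those within 48 hours of a dose. If they do not and the counts cannot be abstracted, drop the ABR label and report only the percentage who bled.

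The cost is SAP wording and a few lines of code, plus any chart abstraction that step 5 shows to be needed. Duration of prophylactic administration is already summarised under SAP 6.5, so the dates behind person-time should be available. One drawback is that short observation makes individual ABRs unstable: one bleed in 30 days gives 365.25/30 ≈ 12.2 per year. The median and the pooled rate handle this.

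### On-demand efficacy is tested and modelled only as any response versus No response, which ignores the order within the collected 4-point scale and has little power if No response is uncommon

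*SAP*

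**What the plan says.** Protocol 7.3.4 and SAP 4.7 define on-demand response as an ordered score from 1 (Excellent) to 4 (No response), the "4 point scale: excellent, good, moderate, and no response". Protocol 7.3.3 and 7.7.1 list the response on those four levels and define no two-level version.

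SAP 6.7(1) and (2) tabulate all four levels, for surgery and for bleeding, using "The best responses to all the injection of the Xyntha Solofuse prefilled syringe used to treat bleeding". SAP 6.7(4) then reduces on-demand response to two classes:

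- effective: "Subjects with whom the best responses 'Excellent' or 'Good' or 'Moderate";
- not effective: "Subjects with whom the best responses 'No response".

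All the inference that follows uses the two classes. Item 5 plans chi-square or Fisher tests "To identify statistically significant difference of frequency distribution of classified overall assessment (effective/not-effective) among demography and baseline characteristics", and item 6 does the same for concomitant treatment and therapy. In item 7, "Logistic regression analysis of multivariate analysis will be performed and presented an odds ratio with 95% confidence interval", again on the two-level outcome. SAP 5.1 sets a two-sided 5% level. No test or model uses the four levels or another cut, and the SAP gives no reason for this one.

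**The concern.** Items 5-7 are meant to find factors associated with efficacy. The flag gives the same value to a subject with clear relief inside 8 hours and no further infusion (Excellent) and to one with "Probable or slight improvement starting after 8 hours following the infusion, with at least one additional infusion administered" (Moderate). A factor that shifts subjects between those levels and leaves No response unchanged cannot show up in the planned tests.

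The only level kept apart may also be a rare one. Because 6.7 takes each subject's best response, a subject is not effective only if every rated infusion failed. If few subjects meet that condition, the tests will usually be non-significant whatever the factor does. The SAP commits to printing the p-values, so a reader of the report could take those results as evidence that no factor matters.

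**Working it through.** The plan has no power figure to reproduce: Protocol 7.5 and SAP 2.4 both say a sample-size calculation does not apply.

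**Inputs from the documents.** Two-sided 5% (SAP 5.1); at least 86 subjects over both regimens (Protocol 5 and 7.5); the two-level cut (SAP 6.7(4)).

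**Assumptions.** All 86 subjects on-demand; a two-level factor splitting them 43 v 43; a common odds ratio (OR) of 3; reference distributions Excellent/Good/Moderate/No response as in the table.

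**Step 1: No-response rate in the comparison group.** p1 = 3o/(1+3o), with o = p0/(1-p0). For p0 = 10%, o = 0.111, so p1 = 0.333/1.333 = 25%. Likewise 2% becomes 5.8%, 5% becomes 13.6% and 20% becomes 42.9%.

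**Step 2: power.** Fisher's test on the flag by exact enumeration; tie-corrected Wilcoxon test on scores 1-4 by simulation. Wilcoxon results from separate runs differ by one to three points.

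| Reference distribution (%) | No response, two groups | Fisher on flag | Wilcoxon on 4 levels |
|---|---|---|---|
| 50/35/13/2 | 2% v 5.8% | 1.6% | 77-80% |
| 40/35/20/5 | 5% v 13.6% | 16% | 78-80% |
| 30/35/25/10 | 10% v 25% | 34% | 78-80% |
| 30/25/25/20 | 20% v 42.9% | 56% | 79-80% |

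Variations at OR 3:

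- With 22 per group, the first three rows become 0.5% v 47%, 6% v 50% and 17% v 50%.
- With a 64 v 22 split, Fisher gives 9%, 25%, 37% and 51% at rates of 2%, 5%, 10% and 20%; Wilcoxon gives 67-69%.
- With a strong ceiling (80/15/4/1%, 43 v 43), the pair is 0.1% v 64%.
- The chi-square approximation, where expected counts allow it, gives about 45% at 10% and 63% at 20% (43 v 43).

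**Step 3: smallest usable count.** With 43 v 43 and all k not-effective subjects in one group, the two-sided Fisher p is 2·C(43,k)/C(86,k).

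- k = 5: 2 × 962,598/34,826,302 = 0.055.
- k = 6: 2 × 6,096,454/470,155,077 = 0.026.

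So with 5 or fewer not-effective subjects, a balanced factor cannot reach p < 0.05. At a uniform rate, the binomial chance of 5 or fewer among 86 is 99% at 2%, 74% at 5%, 13% at 10% and about 0% at 20%. An unbalanced factor can reach significance with fewer.

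**Step 4: events against model size.** The factors named in 6.7(7) need about 9 to 11 parameters: sex 1, age 4 (five groups in SAP 6.1), past/present disease 1-2, renal/hepatic 1-2, concomitant treatment 1 and therapy 1. Expected not-effective subjects are 86 × 0.02 = 1.7, 86 × 0.05 = 4.3 or 86 × 0.10 = 8.6. At these rates the binary model may not be reliably estimable.

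**Step 5: effect of taking the best response.** If infusions were independent with a 20% No-response rate, all of three would fail in 0.2³ = 0.8% of subjects. Independence is a simplification, but it shows why a low subject-level rate is plausible.

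**The case against.** - **The scale is not lost.** SAP 6.7(1)-(2) report all four levels. A reader might infer that the SAP throws the scale away; it does so only for testing and modelling.
- **Almost no power is not a property of the plan.** It depends on a No-response rate that the documents do not give. At 20% and OR 4, Fisher reaches 80% and chi-square 86%, against 94% for Wilcoxon. The gain there is 14 or 8 points. This stands, so the conclusion must be conditional.
- **The tests are not null by construction.** A reader might infer that shifts along the scale can never be seen. Under a common odds ratio the No-response rate moves too (10% to 25% in step 1). A shift is invisible only if it leaves that category unchanged. The simulation also assumes proportional odds, which favours the ordinal test.
- **The 86 are not all on-demand.** The SAP does not say whether items 5-7 pool the regimens. Pooling would add prophylaxis failures, since one atypical bleed within 48 hours makes a prophylaxis subject not effective. The cut at the bottom of the scale is therefore an on-demand feature only. With smaller on-demand groups the ordinal test is also weak, at about 50% with 22 per group.
- **The cut may be required.** No response is the natural failure category, and the protocol builds on-demand LETE from it. Protocol 7.7.2.2 lets the SAP change the planned analysis, and 7.9 ties the SAP to MFDS re-examination guidelines. Those guidelines are not in the documents, and 7.9 does not mention this cut. This is a reason to keep the binary tables, not to make them the only basis for inference.
- **The stakes are limited.** The primary objective is inhibitor detection, and the protocol plans descriptive efficacy with testing only if data are adequate. That limits the severity, but SAP 6.7(5)-(7) still commit to the tests.

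**Conclusion.** The point holds in conditional form. It is certain from the text that the on-demand tests and model ignore every difference among Excellent, Good and Moderate. The size of the power loss is not certain. At 43 v 43 and OR 3, Fisher on the flag gives about 2% at a 2% No-response rate and 56% at 20%, against 77-80% for an ordinal test. Chi-square narrows the gap at 10-20%. The absolute figures are at the upper end, because fewer than 86 subjects may be on-demand.

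The documents do not support saying that the planned tests must fail, or that the gain from an ordinal analysis is large at every response rate. The change is worth making because the data are already collected and the ordinal test had more power in every scenario run. The analyses are secondary and the inhibitor objective is untouched.

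**What to change.** For on-demand subjects, analysed separately from prophylaxis subjects:

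1. In SAP 6.7(5)-(6), base the factor tests on the 4-point subject-level response: Wilcoxon rank-sum for two-level factors and Kruskal-Wallis for factors with more levels.
2. In SAP 6.7(7), use a proportional-odds logistic model on the 4-point response. State how the proportional-odds assumption will be checked, and limit the number of factors to what the on-demand sample supports.
3. Keep the effective/not-effective frequencies in 6.7(4)-(6). If the MFDS format requires the binary test, report it as a secondary result and say so in the SAP.
4. Leave the prophylaxis analysis as it is.

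The cost is revised SAP wording, a few lines of SAS and a sentence explaining the proportional-odds ratio. No new data are needed.
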